13.10 Menorrhagia Impact Questionnaire (MIQ)

Patients will be asked to assess their quality of life and impact of heavy menstrual bleeding (HMB) using a validated patient-reported outcome measurement. This questionnaire measures effects of HMB on limitations in social/leisure activities, physical activities, and ability to work.

The questionnaire will be completed during baseline and at each follow-up visit.

13.11 PBLAC Diaries

Patients will self-report their menstrual blood loss as measured by validated Pictorial Blood Loss Assessment Chart (PBLAC). The 12-month follow-up PBLAC score will comprise the primary endpoint data for this study.

13.11.1 PBLAC Training

During the site initiation visit (SIV) or as needed, the Sponsor or designee will train the authorized study staff to administer the PBLAC education to patients. The study staff will train candidates regarding proper PBLAC completion and assess the patient's understanding.

Conduct PBLAC training early in the screening process, preferably at the first screening visit. The subject will be provided with study materials including the PBLAC diary(ies), instructions and sanitary products. At the subsequent visit, score the PBLAC diary before resuming screening to be assured that the patient has completed it correctly and has a score of \geq 150. Once the patient passes the PBLAC assessment, complete any remaining screening testing.

See **Section 11.4 Rescreening** for details regarding repeating PBLAC training or repeating PBLAC diary administration.

Page 38 of 65

CONFIDENTIAL & PROPRIETARY

13.11.2 Administering PBLAC Diaries

During Screening

If a patient has undergone a procedure (e.g., polyp removal, fibroid removal, IUD removal, etc) that could affect menstrual bleeding, the screening PBLAC may be administered after 30 days from the date of that procedure.

If a patient discontinued taking oral hormonal contraception, the screening PBLAC may be administered after a washout interval of at least 90 days from the last dose of the hormonal contraception.

If a patient is currently on hormonal medication for heavy menstrual bleeding, the patient must discontinue the medication. The screening PBLAC may be administered after a washout interval of at least 90 days from the last dose of the hormonal medication.

During Follow-Up

PBLAC diaries will be distributed and collected through the 12-month follow-up (365 days or 1-year anniversary); accordingly, 13 PBLAC diaries are expected to be collected during the study follow-up. In between visits, participants should return their diaries (in person or by mail) every month upon completion. Electronic scans or photos of diaries are permitted to be submitted monthly, however, the original diaries must still be submitted to the site and retained in the study records as source documents.

At a minimum, the PBLAC diary will be reviewed with the patient at each follow-up visit, and any needed additional sanitary products provided. Confirmation of understanding and/or retraining patients on PBLAC diary completion throughout follow-up is encouraged.

13.11.3 Sanitary Products

The Sponsor will provide the sanitary product inventory for study staff to distribute to each patient. Patients are required to exclusively use the sanitary products provided at screening through the 12-month follow-up visit. Every effort should be made to ensure that all patients comply with this requirement.

13.12 Numerical Rating Scale (NRS)

13.12.1 NRS for Dysmenorrhea-related Pain

Patients will be asked to assess their dysmenorrhea-related pain using an 11-point scale with 0 on one end, representing no pain, and 10 on the other, representing the worst pain ever experienced.

13.12.2 NRS for Procedure-related Pelvic Pain

Patients will be asked to assess their pain level (pelvic pain) experienced at discharge and at the 24-hour contact on a 11-point scale with 0 on one end, representing no pain, and 10 on the other, representing the worst pain ever experienced.

13.13 Patient Global Evaluation

Each patient will be asked to report their satisfaction with the study treatment using a 5-point categorical scale: Very Satisfied, Satisfied, Not Sure, Dissatisfied, Very Dissatisfied.

Page 39 of 65

CONFIDENTIAL & PROPRIETARY

This will be assessed at all follow-up visits up, starting at the 3-month follow-up.

13.14 Investigator Global Evaluation

The investigator or designee will report their satisfaction with the patients' study treatment using a 5-point categorical scale: Very Satisfied, Satisfied, Not Sure, Dissatisfied, Very Dissatisfied.

13.15 Device-related Issues or Device Deficiency/Malfunction

A device-related issue or device deficiency/malfunction is a failure of the device to meet its performance specifications or otherwise perform as intended.

During device set-up, treatment administration and post-treatment, site personnel and/or the PI will be requested to inspect and identify any defective parts. The study Investigator (or designee) will keep documentation, notify the Sponsor and comply with Sponsor procedures for returned goods.

13.16 Minitouch Procedure

The Investigator is to confirm patient eligibility prior to initiating the procedure. The Minitouch procedure is to be performed after the PI and any other delegated investigator have undergone the necessary training. The PI/sub-investigators will perform the procedure in accordance with the IFU and this protocol. See **Section 12.4 Procedure (Day 0) – Enrollment / Discharge,** for guidance on the sequence of events for this visit.

13.16.1 Investigational Devices

Refer to Section 18.3 Investigational Devices for details.

13.16.2 Support

The research coordinator should be present during the procedures to ensure that the study data are collected. A Sponsor-designated technical support person may be present for the clinical procedure as support for the investigator.

13.16.3 Procedure Medications

The use and type of anesthesia is up to the discretion of the investigator and anesthesiologist. This may include, but is not limited to, general, local (e.g., paracervical block) and/or IV sedation. Pre-procedure prophylactic administration of over-the-counter NSAIDs and/or analgesics should also be considered for pain management.

Eligible patients will receive a single treatment, meaning the procedure is completed one time in one clinical setting. Single treatment includes four scenarios:

- a. Analgesic Regimen (No Sedation or Anesthesia)
 - b. Sedation Regimen
 - c. Single Anesthesia Regimen¹
 - d. Multiple Anesthesia Regimen

Page 40 of 65

¹ Patient completes treatment with one anesthesia regimen. Intermittent pauses in between energy delivery will be allowed to manage patient pain and to allow for U-value to increase if it drops to less than 40 during procedure.

May not be reproduced, disclosed, or used in any form or by any means without written permission of an authorized representative of MicroCube, LLC. Hardcopies for reference only.

Record all medications provided prior to, during and after the procedure. Determine if all prescribed preand post-procedure medications were taken. Inquire about the use of non-prescribed pain medication.

Medications will be documented in the EDC (Concomitant Medication eCRF).

14 ADVERSE EVENT REPORTING

14.1 Adverse Event Definitions

14.1.1 Adverse Event (AE):

An adverse event (AE) is any untoward medical occurrence in a study patient which does not necessarily have a causal relationship with the medical device. This includes any unfavorable and unintended sign (including an abnormal, clinically significant laboratory finding), symptom, or disease temporally associated with the use of a medical device, whether or not related to the medical device. It also includes any pre-existing condition that increases in intensity or severity or any new events after the patient had the procedure. (Also refer to Sections 14.1.5 and 14.1.6 for additional information.)

14.1.2 Serious Adverse Events (SAEs)

A serious adverse event is any untoward medical occurrence that results in one of the following:

- Led to death
- Led to serious deterioration in the health of the subject, that either resulted in
 - A life-threatening illness or injury, or
 - o A permanent impairment of a body structure or a body function, or
 - o In-patient hospitalization or prolongation, or
 - Medical or surgical intervention to prevent life-threatening illness or injury or permanent impairment to a body structure or a body function,
- Led to fetal distress, fetal death, congenital abnormality or birth defect
- Note: Planned hospitalization for a pre-existing condition or a procedure required by the protocol, without serious deterioration in health, is not considered a serious adverse event.

14.1.3 Anticipated Adverse Device Effects Associated with Endometrial Ablation

With all endometrial ablation procedures, serious injury or death can occur. The following adverse effects could occur or have been reported in other EA studies and may occur when the Minitouch System is used. The listing includes potential risks/effects associated with administration of anesthesia.

Table 14-1: Anticipated Adverse Device Effects of Endometrial Ablation

More Commonly Reported Device/Procedural and/or Post-Procedural Complications (occurs in 20 or more patients out of 100)

- Cramping or pelvic pain
- Nausea and vomiting
- Vaginal bleeding or spotting
- Vaginal discharge and/or unpleasant vaginal smell or burning or other abnormal sensation

Other Common Possible Adverse Device Effects (occurs in 20 or less patients out of 100)

- Abdominal pain or bloating
- Adhesions
- Backache
- Cervical stenosis
- Chills
- Constipation
- Diarrhea
- Fever
- Headache
- Hematometra (collection of blood in the uterus)
- Lightheadedness or fainting
- Menometrorrhagia (abnormally heavy, prolonged and irregular uterine bleeding)
- Post-ablation tubal sterilization syndrome (PATSS)
- Skin rash and/or itching burning sensation
- Weakness, fatigue, sleepiness, lack of concentration, dizziness

Rare Adverse Device Effects (occurs in 5 or less patients out of 100)

- Agitation
- Air embolism (blood vessel blockage caused by an air bubble)
- Cardiac complications
- Cervical or vaginal laceration or tear
- Complications leading to serious injury or death
- Difficulty with defecation or micturition
- Dyspareunia (painful intercourse)
- Dysuria (painful urination)
- Endometritis or Endomyometritis (inflammation of the uterine tissue)
- Hemorrhage (excessive bleeding)
- Hydrosalpinx (blocked fallopian tubes filled with fluid)
- Infection or sepsis
- Pelvic inflammatory disease (PID)
- Pregnancy-related complications
- Tissue injury (thermal, mechanical or electrical)
- Uterine necrosis (uterine tissue death due to lack of blood supply)

Page 42 of 65

- Uterine perforation (hole in the uterus)
- Vulvar pruritis (itchiness of the vulva)

14.1.4 Unanticipated Adverse Device Effects (UADEs)

Any serious adverse effect on health or safety, any life-threatening problem or death caused by, or associated with a device, if that effect, problem, or death was not previously identified in nature, severity, or degree of incidence in the application; or any other unanticipated serious problem associated with a device that relates to the rights, safety, or welfare of patients per 21 CFR 812.3 and ISO 14155.

14.1.5 Not Adverse Events

- Pre-existing Conditions: Any condition that is recorded in medical records and diagnosed prior to the Minitouch procedure, is considered a pre-existing condition. This condition is not considered an adverse event unless there is a clinically significant worsening of that condition in terms of nature, severity, or degree of incidence. For example, if a patient experiences HMB prior to procedure [e.g., PBLAC score = 300] and continues to experience HMB post-procedure [e.g., PBLAC score = 150 or ≤ 300], this is a pre-existing condition and should not be reported as an adverse event in the study).
- **Device Deficiencies or Malfunctions**: An undesirable device technical event is not an adverse event. However, if a device deficiency or malfunction leads to a medically undesirable situation or an adverse device effect, then that event must be reported on an Adverse Event Form.
- Lack of Effectiveness: Lack of improvement of symptoms is not considered an adverse event.

14.1.6 Adverse Events that do not require reporting to Sponsor

For purposes of the trial, events that are typically expected to occur in and/or are associated with standard of care endometrial ablation therapies are not required to be reported unless they occur with greater severity or intensity than anticipated. Examples of these commonly occurring anticipated post-procedural events include:

- Nausea and vomiting (usually with administration of anesthesia)
- Post-operative pelvic or uterine cramping
- Vaginal discharge (Note: Vaginal discharge usually happens during the first few days following treatment and may last as long as several weeks. It is generally described as bloody during the first few days, a mixture of blood and fluid for another week, then followed by a watery discharge that can be substantial at times. This is an anticipated symptom of the treatment and is not considered an adverse event unless the vaginal discharge suggests infection.)
- Vaginal bleeding/spotting

Note: This listing of events is intended to provide guidance to Investigators for the purpose of adverse event reporting. The investigator should utilize his/her own clinical judgment in evaluating adverse experiences, and may decide that the above events should be reported as adverse events based on site IRB/EC reporting requirements or the subject's clinical condition.

Page 43 of 65

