14.2.3 Other Adverse Events

The Investigator will monitor the occurrence of adverse events for each Patient during the course of the study. All AEs will be listed on the adverse event case report forms. All pre-existing medical conditions and baseline signs and symptoms will be recorded on baseline case report forms for medical history and signs and symptoms.

Adverse events will be monitored until they are adequately resolved or explained.

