17.5 Analysis of All Safety Outcome

All safety events reported in the study will be tabulated. The study's safety analysis focuses on specific device- or procedure-related safety events listed in Section 13. Intra-operative and post-operative serious adverse event (SAE) and overall rates of AEs (number and percentage with 95% confidence interval) will be reported.

The need for medical or surgical intervention to treat abnormal bleeding following the ablation procedure will also be reported.

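### Optional reporting of anticipated post-procedural events under 14.1.6 makes the overall non-serious AE rate and the severity table depend on site practice

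*Combined protocol and SAP*

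**What the plan says.** - **Exemption (14.1.6).** Events expected with standard endometrial ablation "are not required to be reported unless they occur with greater severity or intensity than anticipated". The list is open-ended: "Examples of these commonly occurring anticipated post-procedural events include" nausea and vomiting, pelvic or uterine cramping, vaginal discharge, and vaginal bleeding or spotting.
- **Discretion (14.1.6, note).** The investigator "may decide that the above events should be reported as adverse events based on site IRB/EC reporting requirements", or because of the subject's clinical condition.
- **Discharge (14.1.6).** This one type is treated by definition: it "is not considered an adverse event unless the vaginal discharge suggests infection".
- **Recording (14.2.3).** "All AEs will be listed on the adverse event case report forms". No exception is stated.
- **Analysis (17.5 and 14.2.2).** Section 17.5 says that "overall rates of AEs (number and percentage with 95% confidence interval) will be reported". Section 14.2.2 summarises AEs by severity and by relation to procedure and device. Neither mentions the exemption.
- **Expected frequency (Table 14-1 in 14.1.3).** Cramping or pelvic pain, nausea and vomiting, vaginal bleeding or spotting, and discharge make up the top tier, headed "More Commonly Reported Device/Procedural and/or Post-Procedural Complications (occurs in 20 or more patients out of 100".

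**The concern.** A site cannot follow both 14.1.6 and 14.2.3 for nausea/vomiting, cramping and bleeding/spotting. Section 14.1.6 is headed as a list of adverse events and stands apart from 14.1.5, which lists what is not an adverse event. Some sites will enter these events and others will not, and both can point to the protocol.

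The events concerned are among those the protocol expects most often, so the choice can move the overall figure. The trial has no control arm in which the same habit would cancel out, and section 7.1 says its goal is to support safety compared with approved devices. A reader who sets the overall AE percentage beside another device's figure could be comparing reporting rules.

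**Working it through.** **Step 1: the passages side by side, for a patient with ordinary post-operative cramping.**
- 14.1.1: an untoward occurrence after the procedure, so an AE, with a cross-reference to 14.1.5 and 14.1.6.
- 14.1.6: still called an AE, need not be reported, may be reported.
- 14.2.3: goes on the AE form.
- 17.5 and 14.2.2: counted if entered, absent if not.

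Reading the rules as list it but do not report it does not resolve this. The electronic form is the route to the sponsor: 18.2 puts all study data there, and 14.3 uses it even for SAE notification.

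**Step 2: effect on the overall rate.** The plan states no expected overall AE rate, so there is none to reproduce. What follows is an illustration.

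Inputs:
- N = 126, the planned enrolment (17.2.1), taken here as the AE denominator.
- c = share of patients with at least one of nausea/vomiting, cramping or bleeding/spotting. Discharge is left out because 14.1.6 defines it as not an AE unless it suggests infection. With each type at the 20% boundary of Table 14-1, c = 20% if they fully overlap, 1 − 0.8³ = 48.8% if independent, and 3 × 20% = 60% if disjoint. Which of these applies is an assumption.
- q = share of patients with any other AE, assumed 10% to 30% and independent of c.
- f = share of patients with an exempt-type event for whom it is entered, because it was worse than anticipated or because the site chose to enter it. Assumed 0 to 1. The value 0.35 is shown because 11.7.2 lets one site enrol up to 35% of patients.

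Reported any-AE rate = 1 − (1 − q)(1 − c·f).

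For q = 20% and c = 48.8%, with Clopper-Pearson 95% intervals:

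| f | Calculation | Rate | Count of 126 | 95% CI |
|---|---|---|---|---|
| 0 | 1 − 0.8 × 1 | 20.0% | 25 | 13% to 28% |
| 0.35 | 1 − 0.8 × (1 − 0.1708) | 33.7% | 42 | 25% to 42% |
| 1 | 1 − 0.8 × 0.512 | 59.0% | 74 | 50% to 67% |

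The first and last intervals do not overlap, although the patients' underlying experience is identical. The interval covers sampling error only.

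Moving f from 0 to 1 changes the rate by (1 − q)·c. The smallest value over these ranges is 0.7 × 0.20 = 14 percentage points and the largest is 0.9 × 0.60 = 54 points.

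**Step 3: effect on the severity table.** Let w be the share of these events that are worse than anticipated, all of which must be entered, and r the share of the remainder that are entered. Worse cases then make up w / (w + (1 − w)·r) of the entered events. This equals w only when r = 1, rises as r falls, and is 100% when r = 0. The documents give neither w nor r.

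**The case against.** Much of the other side stands.

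- **Cross-reference.** Section 14.1.1 points to 14.1.6, so the sentence in 14.2.3 can be read subject to it. That softens the contradiction. It does not make collection uniform, because 14.1.6 itself leaves the choice to the investigator and local rules.
- **Reported events.** Sections 9.2 and 17.5 both speak of reported events, so the plan promises a rate of what was reported. That is fair, but neither section tells a reader that a common group of events was optional.
- **Detail left to the SAP.** Section 17 describes itself as an outline of key elements. A later analysis rule could settle which entered events count, but it could not recover events that sites were never required to enter.
- **Other capture.** Procedure-related pelvic pain is scored at baseline, discharge and 24 hours, and menstrual bleeding is recorded in PBLAC diaries. These cover part of the gap, but they do not feed the AE rate, and nausea has no counterpart.
- **Stakes.** No hypothesis or success criterion uses the overall AE rate, and no between-site AE comparison is planned.

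A reader might also infer that at least 20% of patients, or 59% (1 − 0.8⁴, four independent types), are missing from the AE rate. The documents do not support that. Those figures are assumed shares of patients who experience the events. Some cases must be entered as worse than anticipated, others may be entered by choice, and some patients count anyway through another AE. Discharge does not belong in the sum, and independence is unlikely for effects of a single procedure. Table 14-1 also draws on other ablation studies and words some entries more widely than 14.1.6, so its frequencies do not transfer directly.

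**Conclusion.** The point holds for the overall non-serious AE rate and for the severity and relatedness breakdown. As written, both depend on how each site uses the 14.1.6 discretion. The rate will tend to understate AEs as defined in 14.1.1, and the severity table will over-represent the worse cases of the exempted types. The confidence interval reflects neither effect. The conflict is clearest for nausea/vomiting, cramping and bleeding/spotting.

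The size cannot be derived from the documents. The 14 to 54 point range shows only that the effect could be material. It rests on the assumed values of q, the Table 14-1 boundary for each type, and the extremes of no entry and full entry.

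A reader might extend this to the trial's main safety conclusion. That would be wrong: the primary safety endpoint is device- or procedure-related SAEs adjudicated by the CEC, and 14.3 requires every SAE to be reported within 24 hours.

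**What to change.** Reconcile 14.1.6 with 14.2.3 so that one recording instruction applies at every site, and replace the open-ended examples with a closed list. Then take one of two routes.

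1. **One exclusion rule.** In 17.5 and 14.2.2, compute the overall AE rate and the severity table without any non-serious 14.1.6 event that was not worse than anticipated, including those that sites chose to enter. Label the tables accordingly and list the removed events separately. A label alone would be inaccurate while some sites still enter exempt events. The AE form must record whether a 14.1.6 event was worse than anticipated, or the rule cannot be applied. The label should also say that only such cases of these types remain in the severity table.
2. **Uniform capture.** Record the listed types as yes/no items at discharge, the 24-hour contact and Week 2, where AE review is already scheduled, and tabulate them separately from the AE rate.

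The cost is wording in four sections, slightly more form entry, and a qualified rather than unqualified statement of the overall AE rate. No endpoint, sample size or visit changes.

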14.2 Recording Adverse Events

14.2.1 Adverse Event Evaluation and Categorization

All AEs/ADEs will be assessed by the Investigator. Adverse events and Adverse Device Effects will be classified as serious or non-serious. Adverse Events are also qualified by intensity (severity), causality (relatedness), and expectedness.

14.2.2 Intensity (Severity)

- **Mild**: Mild or transient discomfort, without limitation or normal daily activities; no medical intervention or corrective treatment required
- **Moderate**: Mild to moderate limitation of normal daily activities; minimal medical intervention or corrective treatment required
- **Severe**: Marked limitation of normal daily activities; medical intervention and corrective treatment required; possible hospitalization.

Prior to analysis, all adverse events (AEs) will be coded using the Medical Dictionary for Regulatory Activities (MedDRA). Based on these coded terms, treatment emergent AEs will be summarized by treatment period, by severity, relation to procedure and relation to device.

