14.2.4 Determination of the Relationship (Causality)

The Investigator, on the basis of his or her clinical judgment, should determine whether there is a reasonable possibility the investigational device or procedure caused or contributed to the event. Guidelines to assess AE/SAE/UADE are provided below:

Unrelated: The adverse event is determined to be solely caused by the underlying disease, disorder or condition of the patient, or attributable solely to other extraneous causes (unrelated to the device, device malfunction, or the procedure).

Possibly related: The adverse event has onset within a clinically relevant temporal relationship to exposure to the device or procedure and is plausibly at least partially caused by or aggravated by the use of the device, device malfunction, or the procedure. It must also meet one of the following criteria: (1) follows a known or easily foreseen pattern of response to device use or procedure and (2) is not fully attributable to the underlying disease, disorder or condition of the patient, or attributable to other extraneous causes.

Probably related: The adverse event has onset within a clinically relevant temporal relationship to exposure to the device or procedure and is more likely than not to be at least partially caused by or aggravated by the use of the device, device malfunction, or the procedure. It must also meet both of the following criteria: (1) follows a known or easily foreseen pattern of response to device use or procedure; and (2) is not fully attributable to the underlying disease, disorder or condition of the

CONFIDENTIAL & PROPRIETARY

patient, or attributable to other extraneous causes. In addition, if the adverse effect is reversible upon reoperation or device exchange, and such a procedure is done, the effect disappears or lessens in severity within the expected time interval.

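### Section 14.2.2 plans AE summaries by relation to procedure and by relation to device, but the causality levels in 14.2.4 combine the two, so the summaries would not differ

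*Combined protocol and SAP*

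**What the plan says.** Section 14.2.2, after defining the severity grades, describes the AE tables: "treatment emergent AEs will be summarized by treatment period, by severity, relation to procedure and relation to device". Relation to procedure and relation to device are named as separate classifiers.

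Section 14.2.1 lists what is assessed for each event: "Adverse Events are also qualified by intensity (severity), causality (relatedness), and expectedness". Causality appears once and is not divided by source.

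Section 14.2.4 says how causality is judged. The investigator "should determine whether there is a reasonable possibility the investigational device or procedure caused or contributed to the event". Four levels follow, each worded for the combined exposure. The lowest level covers events that are "unrelated to the device, device malfunction, or the procedure". The next requires an event to be "plausibly at least partially caused by or aggravated by the use of the device, device malfunction, or the procedure". The probable and definite levels use the same three-part list.

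Sections 9.2 and 17.4 define the primary safety endpoint as SAEs related to the device or to the procedure. Section 15 leaves the CEC's operating procedures to a separate charter.

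**The concern.** A table by relation to device needs a variable that can differ between a device event and a purely procedural one. The protocol promises such a table, but the only causality scale it defines does not make that distinction. If sites follow 14.2.4 literally, the column for relation to device will include events in which the device played no part, and it will match the column for relation to procedure.

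At stake is whether the report can state a device-related AE rate. Section 7.1 gives the goal as supporting the reasonable safety of the investigational product. The trial has a single arm, so no comparison group can show which events come with any ablation procedure and which come with this device.

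**Working it through.** No figure in the plan is in dispute, and no arithmetic applies. The check compares the variable that 14.2.2 needs with the one that 14.2.4 defines.

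**Step 1: possible causes.** An event can be caused by the device only (including malfunction), by the procedure only, by both, or by neither.

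**Step 2: rate each type under both rules.**

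| True cause | Device rating needed by 14.2.2 | Procedure rating needed by 14.2.2 | Rating under 14.2.4 as worded |
|---|---|---|---|
| Device only | related | unrelated | related |
| Procedure only | unrelated | related | related |
| Both | related | related | related |
| Neither | unrelated | unrelated | unrelated |

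The last column is related whenever either of the two middle columns is related. Three different patterns therefore share one value, and the middle columns cannot be recovered from it.

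**Step 3: would asking twice help?** Take the procedure-only row and ask about the device. The unrelated level requires the event to be "unrelated to the device, device malfunction, or the procedure". The event is related to the procedure, so this level is closed. The possible level accepts an event that is "plausibly at least partially caused by or aggravated by the use of the device, device malfunction, or the procedure", which a procedural event meets through its last term. The written levels thus give the same answer on both passes. A second field alone, with the wording unchanged, does not produce two different tables.

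**Step 4: which results depend on the split?**
- Primary safety endpoint (9.2, 17.4): related to device or procedure. This is the last column of the table, so the combined rating yields it correctly.
- Safety measures at 24 and 36 months (7.2.1, 9.3) and the focus of the safety analysis in 17.5: also worded with the combined term.
- Breakdowns by relation to procedure and by relation to device (14.2.2): these need the two middle columns and cannot be built.

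**Step 5: size.** The documents give no division of related events between device and procedure. From the combined rating alone, the device-related rate could lie anywhere from zero (every related event procedure-only) to the full combined rate (every related event at least partly due to the device). No narrower range can be supported.

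**The case against.** The best counter-argument is that two ratings were intended all along. Section 14.2.2 names two variables, 14.2.4 calls its levels guidelines, and nothing in the text says that causality is entered only once. The AE case report form and the CEC charter are not in the documents and may carry separate fields. An investigator asked about the device could sensibly apply only the device part of each definition. This stands as far as intent goes: it cannot be claimed that the trial's forms hold a single field. It does not remove the conflict, because the only written definitions point the other way, and sites that apply them literally will differ from sites that adapt them.

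It is also fair to say that the consequence is small. No hypothesis or success criterion uses a device-only rate. That stands.

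A reader might infer two stronger points, which the documents do not support:

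- *That UADEs cannot be identified.* Section 14.1.4 defines them on its own terms, as serious effects "caused by, or associated with a device" that were not previously identified, and 14.3 gives them their own reporting and sponsor evaluation. Nothing says that they are read from the 14.2.4 scale.
- *That anesthesia harm will be counted as device harm.* Section 13.16.3 says that "The use and type of anesthesia is up to the discretion of the investigator and anesthesiologist", so the mix of regimens will vary. But 14.2.4 does not mention anesthesia. Section 14.1.3 includes its effects among the anticipated device effects, which leans toward pooling, yet a rater could equally treat an anesthetic reaction as an extraneous cause. Regimen and procedure medications are recorded and AEs are MedDRA-coded, so events can still be tabulated by term and by regimen.

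**Conclusion.** The conflict is real and should be corrected, but it is modest in size. As written, 14.2.4 cannot supply the two breakdowns that 14.2.2 promises: a procedure-only event would appear as related in both, the two tables would not differ, and a device-related AE rate could not be reported. The effect is limited to descriptive AE tables. The primary safety endpoint and the combined safety measures at 24 and 36 months stand as planned.

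The conclusion assumes that raters follow the level definitions literally. If the unseen form already has separate device and procedure fields, less needs changing, but the wording of the levels still does. No numerical distortion is claimed, because the documents give nothing from which to derive one.

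**What to change.** In 14.2.4, state that each AE is rated twice on the four levels: once for relation to the device, including malfunction, and once for relation to the procedure. Give each rating its own level wording, so that an event due only to the procedure can be rated unrelated to the device. State whether anesthesia belongs under procedure.

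Record both ratings on the eCRF and in CEC adjudication if they are not already there, and build the 14.2.2 tables from them. Count an SAE toward the primary safety endpoint if it is related on either rating. This keeps the endpoint as 9.2 and 17.4 define it, and settles the synopsis, which joins the two terms with *and* rather than *or*.

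The cost is at most one added eCRF field, a wording change and slightly more rating work per event. No visits or staff are added. If the sponsor does not want a device-only rate, the lighter alternative is to change 14.2.2 to one combined summary. That removes the contradiction but gives up the device-specific table.
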